10.8.2. Individual Dose Titration Rules for NTD Patients in the Expansion Cohort

For the expansion cohort, the starting dose to be administered on Cycle 1 Day 1 for NTD patients will be determined by the sponsor in conjunction with the SRT (see [Table 2](#)). For subsequent cycles, dose level may be titrated individually for each patient. For all NTD patients the dose level will be assessed for titration at C3D1, C4D1, and C5D1. The dose level should be titrated individually for each patient not to exceed the maximum dose level evaluated as follows:

- If hemoglobin increase from baseline is < 1.5 g/dL throughout the previous 2 cycles at the same dose level, the dose level will be increased by 1 dose level (unless dose modification is required).
- If hemoglobin increase from baseline is ≥ 1.5 g/dL but not sustained for at least 2 consecutive measurements during the previous 2 cycles at the same dose level, the dose level will be increased by 1 dose level (unless dose modification is required).
- If hemoglobin increase from baseline is ≥ 1.5 g/dL for at least 2 consecutive measurements during the previous 2 cycles at the same dose level, the dose level will be unchanged (unless dose modification is required).

Baseline hemoglobin to assess titration will be the average of 2 or more measurements performed during the screening period. Hemoglobin measurements within 2 weeks following RBC transfusion will be excluded from the both the calculated mean baseline hemoglobin and on study values used for evaluating dose titration for a patient.

10.8.3. Individual Dose Titration Rules for TD Patients in the Expansion Cohort

For the expansion cohort, the starting dose to be administered on Cycle 1 Day 1 for TD patients will be determined by the sponsor in conjunction with the SRT (see [Table 2](#)[Table 2](#)). For subsequent cycles, the dose level may be titrated individually for each patient. For all TD patients the dose level will be assessed for titration at C3D1, C4D1, and C5D1. The dose level should be titrated individually for each patient not to exceed the maximum dose level evaluated as follows:

- If patient is transfused with ≥ 3 units during the previous 2 cycles at the same dose level, the dose level will be increased by 1 dose level (unless a dose modification is required)

A dose delay and/or dose reduction may be required for individual patients as outlined in the Patient Dose Modification Rules ([Section 10.8.1](#)). The SRT will meet periodically to monitor overall safety and erythroid response data for the expansion cohort.

10.8.4. Other Considerations for Dose Modification, Delay or Discontinuation

For individual patients judged by the investigator to be at an unacceptable risk, but who do not meet the protocol-defined conditions for a dose modification, the investigator should consult with the medical monitor to decide whether to continue dosing at the same dose level, reduce the dose level, or discontinue the patient's treatment with ACE-536.

11. STUDY PROCEDURES

Please refer to [Section 2](#) for the schedule of procedures required for each visit.

11.1. Written Informed Consent

Patients will be required to sign an IEC approved ICF prior to any study related procedures, including screening evaluations.

11.2. Clinical Laboratory Tests

The following laboratory assessments will be performed at the clinical site's local laboratory according to the laboratory collection recommendations. The sponsor may request additional safety tests be performed based on ongoing data review during the study.

- Hematology: RBC, WBC with differential, hemoglobin, hematocrit, haptoglobin (optional), reticulocyte count, platelet count, MCV, MCH, MCHC, and RDW.
- Serum chemistry: Sodium, potassium, chloride, carbon dioxide/bicarbonate (optional), AST, ALT, lactate dehydrogenase (LDH), total bilirubin, indirect bilirubin, alkaline phosphatase, blood urea nitrogen (BUN)/urea, creatinine, GGT, calcium, phosphorus, glucose, amylase, lipase, total protein, albumin, and uric acid.
- Urinalysis by dipstick analysis: pH, specific gravity, protein, glucose, ketones, blood, leukocyte esterase, and nitrite, with microscopic examination if indicated.
- Pregnancy test (urine or serum) and menstrual history for women of child bearing potential.
- Screening visit only: serum folate, B₁₂

The following laboratory assessments will be performed at the central laboratory according to the laboratory collection recommendations. The sponsor may request additional safety tests be performed based on ongoing data review during the study.

- Iron studies: Serum iron, TIBC, transferrin, soluble transferrin receptor, ferritin, NTBI, and hepcidin.
- nRBCs
- Erythropoietin levels
- Peripheral blood smear
- Hemoglobin electrophoresis, globin chain mRNA
- Urine microalbumin and creatinine
- Bone Biomarkers: serum BSAP and CTX

11.3. Other Safety Assessments

- Physical examination (including optional evaluation of gonadal size in males)

- Vital signs: weight, heart rate, systolic and diastolic blood pressure, respiration rate, and temperature (measured in degrees Celsius). Height is measured only at screening. If at any visit the systolic blood pressure is ≥ 150 mmHg, the diastolic blood pressure is ≥ 95 mmHg, and/or the absolute increase in either measure from baseline is ≥ 20 mmHg, perform one repeat blood pressure assessment after a minimum of 15 minutes.
- 12-lead ECG
- Anti-drug antibody testing
- Abdominal ultrasound should be performed as needed for patients with clinical signs of a change in spleen size or abnormality in the dose escalation cohorts only.

11.4. Pharmacokinetic and Pharmacodynamic Assessments

11.4.1. Pharmacokinetic Assessments

Pharmacokinetic assessment of ACE-536 concentrations will be performed periodically as outlined in [Section 2](#). Blood samples should be drawn and processed on-site for serum collection at the time points specified. Additional details regarding PK collection and processing can be found in the Study Reference Guide.

11.4.2. Pharmacodynamic Evaluations

Pharmacodynamic assessments including hematologic laboratory assessments and transfusion information will be used to determine erythroid response to ACE-536.

An MRI will be performed at selected sites to evaluate liver iron content (all cohorts), EMH mass size (expansion cohort only), and spleen size (expansion cohort only).

A DXA will be performed at selected sites to evaluate total body, lumbar spine and total hip BMD (expansion cohort only).

Leg ulcer(s) size will be assessed in patients with leg ulcers; photographs should be taken to document changes.

A 6MWT will be performed at selected sites (expansion cohort only) for NTD patients.

An abdominal ultrasound of the spleen will be performed to evaluate spleen size for patients without a history of splenectomy in the dose escalation cohorts only.

Biomarkers for iron metabolism will include serum iron, TIBC, transferrin, soluble transferrin receptor, ferritin, NTBI, and hepcidin.

Biomarkers for bone metabolism will include serum CTX (a marker of bone resorption) and BSAP (a marker of bone formation).

Biomarkers related to the TGF- β superfamily, such as GDF15, may be tested in blood (to be determined). The relationship of biomarkers to erythroid response may be investigated.

The relationship of biomarkers to erythroid response may be investigated.

The sponsor may request additional biomarkers for exploratory research purposes only.

Quality of Life tools including but not limited to the FACT-An and SF-36 questionnaires will be assessed.

12. STUDY SCHEDULE

Please refer to [Section 2](#) for the schedule of procedures required for each visit. Note that all windows on visits should be determined relative to the date of the previous dose of ACE-536.

12.1. Screening

- Signature of the current IEC approved ICF should occur prior to initiation of any study-specific screening procedures.
- All screening procedures should occur within 28 days prior to Cycle 1 Day 1.
- Screening MRI for liver iron content (all cohorts at selected sites), MRI of the chest and abdomen for EMH masses (expansion cohort only at selected sites), MRI for spleen (if no prior splenectomy; expansion cohort only at selected sites), abdominal ultrasound of the spleen (if no prior splenectomy; dose escalation cohorts only) and ECHO, MUGA or cardiac MRI (all cohorts) can be performed up to 56 days prior to Cycle 1 Day 1. If performed as part of standard of care, it does not need to be repeated.
- Historical hemoglobin values will be collected for 12 weeks prior to Cycle 1 Day 1. Historical transfusion history will be collected for 12 months prior to Cycle 1 Day 1.
- Baseline hemoglobin will be the average of two measurements; one performed within one day prior to Cycle 1 Day 1, and the other performed during the screening period (Day -28 to Day -1).
- Pregnancy test (urine or serum) and menstrual history is required of female patients of child bearing potential only.
- Concomitant medications taken within 28 days prior to Cycle 1 Day 1 will be documented in the CRF.
- Screen failure information will be maintained to document specific information, including but not limited to, reason for failure.
- For the expansion cohort patients only, administration of quality of life questionnaires.
- For blood pressure measurements, if the systolic blood pressure is ≥ 150 mmHg, the diastolic blood pressure is ≥ 95 mmHg, and/or the absolute increase in either measure from baseline is ≥ 20 mmHg, perform one repeat blood pressure assessment after a minimum of 15 minutes.

12.2. Dosing Days and Interim Visits

- For the first dose of ACE-536, dosing should occur after a minimum of 7 days post-transfusion; subsequent doses should not be given within 24 hours of transfusion or planned transfusion.
- Note: For any RBC transfusions received during the study, collect hemoglobin value just prior to transfusion.
- Each TD patient in the expansion cohort will have a baseline “pre-transfusion hemoglobin threshold” which will be calculated based on transfusion history and will be used for determining when to transfuse during the study
- All screening and Cycle 1 Day 1 procedure results required to confirm eligibility must be obtained and reviewed prior to study drug administration. Patient eligibility must be confirmed from these results.
- A patient will be considered enrolled into the study once a multi-digit patient identification number has been assigned to the patient. After assignment of the patient identification number and the completion of the required procedures, study drug administration may occur. Note that the patient dose must be calculated based on the patient’s weight on the day of dosing.
- All study procedures on each dosing day must be done prior to administration of study drug.
- Patients should be observed for a minimum of 30 minutes following treatment with ACE-536.
- If a dose delay is required per the patient dose modification rules (see [Section 10.8.1](#)), the patient will not be dosed. The patient will return weekly for assessment of hematology results and adverse events until the patient is eligible to receive the next dose of ACE-536.
- The hematology results can be collected up to 24 hours prior to the dosing day. For Cycle 1 Day 1, the hemoglobin should be available to confirm eligibility within one day prior.
- Any non-serious AEs that occur prior to dosing on Cycle 1 Day 1 should be recorded in the Medical History CRF.
- All AEs that occur after dosing on Cycle 1 Day 1 should be recorded in the AE CRF.
- On subsequent dosing days, all AEs and abnormal findings that might require modification of dosing (see [Section 10.8](#)) should be reviewed prior to dosing to ensure that the patient is still eligible to receive additional doses of ACE-536.
- Pregnancy test (urine or serum) and menstrual history is required of female patients of child bearing potential only.
- Physical exam on Cycle 1 Day 1 should include an optional evaluation of gonadal size of male patients.

- For blood pressure measurements, if the systolic blood pressure is ≥ 150 mmHg, the diastolic blood pressure is ≥ 95 mmHg, and/or the absolute increase in either measure from baseline is ≥ 20 mmHg, perform one repeat blood pressure assessment after a minimum of 15 minutes.
- Leg ulcer(s) size will be assessed in patients with leg ulcers; photographs should be taken to document changes.

12.3. Day 85

- Day 85 (± 2 days) is the last possible study day that ACE-536 may be administered, regardless of the cycle.
- For the expansion cohort patients only, administration of quality of life questionnaires.
- For blood pressure measurements, if the systolic blood pressure is ≥ 150 mmHg, the diastolic blood pressure is ≥ 95 mmHg, and/or the absolute increase in either measure from baseline is ≥ 20 mmHg, perform one repeat blood pressure assessment after a minimum of 15 minutes.

12.4. End of Treatment Visit

- The end of treatment visit should occur approximately 28 days after the last dose of ACE-536.
- Patients who discontinue treatment early should complete the end of treatment visit at the time of discontinuation.
- Patients in the expansion cohort who discontinue treatment early or do not complete the Day 85 visit should complete the quality of life questionnaires at the end of treatment visit.
- An abdominal ultrasound of the spleen will be performed for patients without a history of splenectomy in the dose escalation cohorts only.
- An MRI will be performed at selected sites to evaluate liver iron content (all cohorts), and an MRI of the chest and abdomen for EMH mass size (expansion cohort only), and spleen size (expansion cohort only).
- A DXA will be performed at selected sites to evaluate total body, lumbar spine and total hip BMD (expansion cohort only).
- A 6MWT will be performed in NTD patients at selected sites (expansion cohort only).
- Leg ulcer(s) size will be assessed in patients with leg ulcers; photographs should be taken to document changes.
- Pregnancy test (urine or serum) and menstrual history will be collected for women of child bearing potential.
- Physical exam should include an optional evaluation of gonadal size of male patients.

- For blood pressure measurements, if the systolic blood pressure is ≥ 150 mmHg, the diastolic blood pressure is ≥ 95 mmHg, and/or the absolute increase in either measure from baseline is ≥ 20 mmHg, perform one repeat blood pressure assessment after a minimum of 15 minutes.

12.5. End of Study Visit

- The end of study visit should occur approximately 28 days after the end of treatment visit.
- Patients who discontinue treatment early should complete the end of study visit approximately 28 days after the end of treatment visit.
- For the expansion cohort patients only, administration of quality of life questionnaires.
- If a patient has a positive anti-drug antibody (ADA) result at the last visit, the patient may be asked to return for additional ADA testing every three months, until a negative result is obtained or the result is considered to be stabilized.
- Menstrual history will be collected for women of child bearing potential; pregnancy test not required.
- Physical exam should include an optional evaluation of gonadal size of male patients.
- For blood pressure measurements, if the systolic blood pressure is ≥ 150 mmHg, the diastolic blood pressure is ≥ 95 mmHg, and/or the absolute increase in either measure from baseline is ≥ 20 mmHg, perform one repeat blood pressure assessment after a minimum of 15 minutes.
- Leg ulcer(s) size will be assessed in patients with leg ulcers; photographs should be taken to document changes.

12.6. Termination of Study

The sponsor may terminate this study or discontinue a cohort, after consultation with the investigator(s), or at any time, for safety or administrative reasons. The sponsor will terminate the study if the occurrence of SAEs or other findings suggests unacceptable risk to the health of the patients.

13. STUDY DRUG MATERIALS AND MANAGEMENT

13.1. Study Drug

ACE-536 is a recombinant fusion protein consisting of a modified form of the extracellular domain (ECD) of the human activin receptor IIB (ActRIIB) linked to the human IgG1 Fc domain.

13.2. Study Drug Packaging and Labeling

ACE-536 drug product is provided as a sterile, liquid formulation at a nominal concentration of 50 mg/mL in Tris-buffered saline, pH 7.2 ± 0.5 , contained in type I, 13-mm borosilicate glass vials (stoppered and crimp-sealed). Each single-use vial contains 0.5 mL (25 mg) of ACE-536 solution for injection.

13.3. Study Drug Storage

ACE-536 is stored frozen at $\leq -65^{\circ}\text{C}$ until use.

13.4. Study Drug Preparation

Please refer to the Study Reference Guide, provided under separate cover, for detailed ACE-536 drug handling, administration, and storage instructions.

13.5. Study Drug Administration

ACE-536 will be administered by SC injection. Multiple injections may be required to administer the appropriate dose at higher dose levels; however, no more than 3 injections will be administered per dose. Patients should be observed for a minimum of 30 minutes following treatment with ACE-536.

13.6. Study Drug Accountability

Accountability for ACE-536 is the responsibility of the investigator. Investigational clinical supplies must be received by a designated person at the clinical site and kept in a secured location. The clinical site must maintain accurate records demonstrating dates and amounts of ACE-536 received, to whom it was dispensed (patient-by-patient accounting), and accounts of any ACE-536 accidentally or deliberately destroyed or returned.

Unless otherwise notified, all vials of ACE-536, both used and unused, must be saved for drug accountability purposes. The used vials may be discarded, per the institution's standard practice, after drug accountability assessment has been completed by the clinical monitor. At the end of the study, the sponsor will provide direction for the outcome of all unused vials. Following on the sponsor's instructions, the investigator must either return all unused vials of ACE-536 to the sponsor or destroy them at the clinical site. In either case, the outcome must be documented on the drug accountability log.

13.7. Study Drug Handling and Disposal

Please refer to the Study Reference Guide, provided under separate cover, for detailed ACE-536 drug handling, administration, storage, and disposal instructions.

14. ASSESSMENT OF SAFETY

14.1. Adverse Event Definitions

Adverse Event

An adverse event (AE) is any untoward medical occurrence in a patient or clinical investigation patient administered a study drug, which does not necessarily have a causal relationship with this treatment. An AE can therefore be any unfavorable and unintended sign (including an abnormal laboratory finding), symptom, or disease temporally associated with the use of the study drug whether or not it is considered related to the study drug.

Abnormal laboratory and other abnormal investigational findings (e.g., physical exam, ECG) should not be reported as AEs unless they are associated with clinical signs and symptoms, lead to treatment discontinuation, or are otherwise considered clinically relevant by the investigator. In cases of surgical or diagnostic procedures, the condition/illness leading to such a procedure is considered as the AE rather than the procedure itself. In case of a fatality, the cause of death is considered as the AE, and the death is considered as its outcome.

Unexpected Adverse Events

An unexpected AE is an AE that is not described in nature or severity in the Investigator's Brochure.

Events Not to Be Considered as Adverse Events

Pre-existing medical conditions/signs/symptoms present before the Screening period that do not worsen in severity or frequency during the study are defined as Baseline Medical Conditions, and are not to be considered AEs. Anticipated day-to-day fluctuations of pre-existing conditions, including the disease under study, that do not represent a clinically significant exacerbation or worsening need not be considered adverse events.

Serious Adverse Event

A serious adverse event (SAE) is any AE, occurring at any dose level/regimen and regardless of causality that:

- Results in death.
- Is life-threatening: Life-threatening means that the patient was at immediate risk of death from the reaction as it occurred (i.e., it does not include a reaction which hypothetically might have caused death had it occurred in a more severe form).
- Requires inpatient hospitalization or prolongation of existing hospitalization; however, a hospitalization for an elective procedure will not be considered an SAE.
- Results in persistent or significant disability/incapacity.

- Is a congenital anomaly/birth defect.
- Is an important medical event: an important medical event is an event that may not result in death, be life-threatening, or require hospitalization, but may be considered an SAE when, based upon appropriate medical judgment, it may jeopardize the patient and may require medical or surgical intervention to prevent one of the outcomes listed in the definitions for SAEs. Examples of such medical events include allergic bronchospasm requiring intensive treatment in an emergency room or at home, blood dyscrasias or convulsions that do not result in inpatient hospitalization, or the development of drug dependency or drug abuse.

For the purposes of reporting, any suspected transmission of an infectious agent via a medicinal product is also considered a serious adverse reaction and all such cases should be reported in expedited manner.

Events Not to Be Considered as Serious Adverse Events

Elective hospitalizations to administer or to simplify study treatment or procedures are not considered SAEs.

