7.4. Potential Risks of Human Use

Increases in hematologic parameters (RBC, hemoglobin, hematocrit, reticulocytes) are expected pharmacologic effects of ACE-536 treatment. Increases in systolic and diastolic blood pressures may occur in concert with increases in hemoglobin values. Excessive or rapid increases in hemoglobin or blood pressure may occur and will be monitored. Dose modifications rules for individual subjects and dose escalation/reduction rules will be utilized to minimize risks associated with increased RBC parameters.

Adverse events observed in the Phase 1 study in healthy volunteers that were considered probably or possibly related to study drug included injection site hemorrhage, injection site macule, dry skin, hyperesthesia, muscle spasms, myalgia, generalized pruritis, and papular rash.

Membranoproliferative glomerulonephritis was observed in both rats and monkeys, likely secondary to immune complex deposition. These findings were associated with increases in serum BUN and creatinine. The presence of immune complexes in renal tissue from monkeys treated with ACE-536 was demonstrated by immunohistochemistry.

The growth of heart and lungs was slightly reduced in rats exposed to ACE-536 as compared with control animals; these decreased heart and lung weights were reversible and there was no

corresponding histology finding. These findings were not replicated in the monkey toxicology studies; the potential for these adverse effects in humans is unknown.

Based on rat toxicology studies, treatment with ACE-536 may affect the adrenal gland. These findings were specific to the rat as they were not replicated in the monkey toxicology studies.

As with all biologics, there is the potential for anti-drug antibodies that can be associated with increased drug clearance and hypersensitivity reactions. Anti-drug antibody formation against ACE-536 as well as human ActRIIB protein will be monitored in the initial clinical studies.

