10.6. Dose-Limiting Toxicity Definition

A Dose-Limiting Toxicity (DLT), using the current active minor version of the National Cancer Institute Common Toxicity Criteria for Adverse Events version 4.0 (NCI-CTCAE v4.0), is defined as any of the following toxicities, at any dose level occurring within 28 days of the first administered dose:

- Treatment related serious adverse event (SAE) of Grade ≥ 3
- Treatment related non-hematologic adverse event (AE) of Grade ≥ 3
- Treatment related hematologic AE of Grade ≥ 4 .

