10.8.1. Patient Dose Modification Rules

The following dose modification rules include both pharmacodynamic and safety parameters which may require a dose delay and possibly a dose reduction. These rules should be assessed prior to dosing. If a dose delay is required the patient should have weekly visits to assess hematology results and adverse events until the patient is eligible to receive the next dose of ACE-536.

Observation on Dosing Day	Action	ACE-536 Dose Modification ^a
Hemoglobin \geq 13 g/dL	Hold dose and monitor patient weekly until hemoglobin $<$ 12 g/dL	Resume dosing once hemoglobin $<$ 12 g/dL.
Hemoglobin increase \geq 2 g/dL from the previous dosing day (not attributable to RBC transfusion)	Continue dosing	Reduce dose by 1 dose level ^b
Non-hematologic adverse event \geq Grade 3, or hematologic adverse event \geq Grade 4, at least possibly related to study drug	Hold dose and monitor patient weekly until resolution of AE to \leq Grade 1 or baseline	Resume dosing upon resolution of the AE to \leq Grade 1 or baseline and reduce dose level by 1 dose level ^b

^a Last possible treatment day is Study Day 85 (\pm 2 days).

^b All subsequent doses will remain at the new dose level or can be reduced further if needed. Patients who require more than 2 dose reductions due to an AE should be discontinued from treatment and complete the end of treatment and end of study visits.

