14.5. Documentation and Methods of Reporting of Adverse Events by Investigator

It is the responsibility of the Investigator to document all adverse events that occur during the study. Patients will be evaluated and questioned generally for AEs during the course of the study, starting at the signing of the informed consent. The Investigator must report in detail all adverse signs and symptoms which are either volunteered by subjects or observed during or following the course of investigational product administration on the appropriate CRF page. All non-serious AEs occurring after signing of the ICF until a patient is dosed on Cycle 1 Day 1 are to be documented on the medical history CRF. All AEs and SAEs occurring after the Cycle 1 Day 1 dose through 56 days after the last study drug administration (End of Study visit) are to be reported and documented on the AE CRF.

All AEs spontaneously reported by the patient and/or in response to an open question from study personnel or revealed by observation, physical examination, or other diagnostic procedures will be recorded on the AE CRF. Any clinically relevant changes in laboratory assessments, or other clinical findings as described in [Section 14.1](#), are considered AEs and must be recorded on the AE CRF. AEs are to be followed for resolution as described in [Section 14.6](#).

It is important that each AE report include a description of the event, duration (onset and resolution dates), severity, relationship with ACE-536, any other potential causal factors, any treatment given or other action taken (including dose modification or discontinuation of ACE-536) and outcome. In addition, serious AEs (SAEs) should be identified and the

appropriate seriousness criteria documented. AEs categorized as SAEs must also be documented using an SAE Report Form as described in [Section 14.5.1](#).

Specific guidance can be found in the CRF Completion Guidelines provided by the Sponsor or designee.

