5.8.1. Dose Limiting Toxicities

A Dose-Limiting Toxicity (DLT) is defined as any of the following toxicities, at any dose level occurring within 28 days of the first administered dose:

- Treatment related serious adverse event (SAE) of Grade \geq 3
- Treatment related non-hematologic adverse event (AE) of Grade \geq 3
- Treatment related hematologic AE of Grade \geq 4

Incidence rates of DLTs will be presented by dose cohort. Details of DLTs will be presented in listings.

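### A symptom-free laboratory value at DLT grade may be missing from the DLT and Grade ≥3 counts, because recording it as an AE rests on investigator judgement and no SAP table counts laboratory grades

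*Protocol*

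**What the plan says.** **When a laboratory value becomes an AE.** Protocol 14.1 gives the default: "Abnormal laboratory and other abnormal investigational findings (e.g., physical exam, ECG) should not be reported as AEs unless they are associated with clinical signs". The same sentence adds findings that "lead to treatment discontinuation, or are otherwise considered clinically relevant by the investigator". Protocol 14.5 makes recording mandatory once relevance is accepted: "Any clinically relevant changes in laboratory assessments, or other clinical findings as described in" section 14.1 are AEs and go on the AE form. Neither section names a grade.

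**What is counted from AEs.** Protocol 10.6 and SAP 5.8.1 define a DLT within 28 days of the first dose as a related SAE of Grade 3 or higher, a related hematologic AE of Grade 4 or higher, or a "Treatment related non-hematologic adverse event (AE) of Grade ≥ 3". In Protocol 10.8.1 the toxicity row starts from a related AE of those grades: "Hold dose and monitor patient weekly until resolution of AE to" Grade 1 or baseline. SAP 5.8.1 states: "Incidence rates of DLTs will be presented by dose cohort". SAP 5.8.2 tabulates patients with Grade ≥3 AEs.

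**The named renal risk.** Protocol 7.4 reports membranoproliferative glomerulonephritis in rats and monkeys: "These findings were associated with increases in serum BUN and creatinine".

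**What the SAP does with laboratory data.** SAP 5.8.3 summarises values and changes by cohort and visit, lists all values, and gives shift tables for hematology and biochemistry. The shift tables use below, within and above normal range, from baseline to end of treatment.

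**The concern.** The safety counts that matter most in a dose-escalation study start from AEs, while the entry of a symptom-free laboratory abnormality into AE reporting depends on a judgement with no objective criterion. Up to 15 open-label centres may make that judgement differently for the same value. A toxicity hold does not help, because the hold itself requires an AE, and 14.1 lists discontinuation but not a hold as a reason to report.

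Cohorts have 3 to 6 patients, and two patients with a DLT are enough for Protocol 10.7 to advise against escalation, so a single unrecorded event can matter. At the reporting stage, DLT incidence and Grade ≥3 rates by cohort could be too low, and no planned table would show it.

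**Working it through.** The plan states no figure on this point. Steps 1 to 4 compare the texts; step 5 is an illustration.

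**1. Routes into AE reporting (Protocol 14.1, 14.5).** Clinical signs and symptoms; treatment discontinuation; clinical relevance as judged by the investigator. For a symptom-free value in a patient who stays on treatment, only the third remains.

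**2. What depends on AE status.**
- DLT count (Protocol 10.6, SAP 5.8.1): yes.
- Toxicity row of Protocol 10.8.1: yes.
- The two hemoglobin rows of 10.8.1: no, they act on the value itself.
- Escalation criteria (Protocol 10.7): two use the DLT count and one uses confirmed hemoglobin increase. No other laboratory parameter has its own criterion.
- Grade ≥3 table (SAP 5.8.2): yes.

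A Grade 3 hematologic value is not a DLT even when recorded, unless it is also a related SAE. The gap therefore concerns non-hematologic Grade ≥3 and hematologic Grade ≥4 values.

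**3. Where laboratory data appear without AE status.** Safety Review Team review of hematology and chemistry (Protocol 10.7); pre-dose review of abnormal findings (Protocol 12.2); consultation with the medical monitor (Protocol 10.8.4); by-visit summaries, shift tables and listings (SAP 5.8.3).

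**4. Tracing one value.** Take a creatinine at DLT grade on Day 15 that has returned to normal by end of treatment, with no symptoms and not judged clinically relevant. After the first dose, chemistry is scheduled on Day 15 and Day 22 within the 28-day window.
- DLT table: absent. Grade ≥3 AE table: absent.
- Shift table: normal to normal, because it uses the end-of-treatment value, about Day 113 for a patient who completes treatment.
- By-visit summary: it affects the Day 15 mean and may be the maximum, but is neither graded nor counted.
- Listing: present as one row among all values.

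**5. Sensitivity of the two-DLT criterion.** Let n be cohort size, p the assumed rate of related, symptom-free laboratory toxicity at DLT grade, and s the assumed share recorded as AEs. With q = p × s, and no other DLTs:

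P(at least 2 counted) = 1 − (1−q)^n − n·q·(1−q)^(n−1)

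For n = 6:
- p = 40%, s = 1 (q = 0.40): 1 − 0.04666 − 0.18662 = 0.767
- p = 40%, s = 0.5 (q = 0.20): 1 − 0.26214 − 0.39322 = 0.34464, or 34%
- p = 10%, s = 1 (q = 0.10): 1 − 0.53144 − 0.35429 = 0.114
- p = 10%, s = 0.5 (q = 0.05): 1 − 0.73509 − 0.23213 = 0.033

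For n = 3, p = 40%:
- s = 1: 1 − 0.216 − 0.432 = 0.352
- s = 0.5: 1 − 0.512 − 0.384 = 0.104

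The documents support neither p nor s.

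**The case against.** The other side has real force. Section 14.1 does not bar symptom-free findings: its own definition of an AE includes an abnormal laboratory finding, it has a clinical-relevance route, and 14.5 makes that route mandatory. Most investigators would call a related Grade 3 creatinine rise clinically relevant. The Safety Review Team reads the chemistry results, applies its criteria only in part, is permitted rather than obliged to escalate when at most one DLT occurs, and may postpone. The only clinical data in the protocol (Section 7.3, healthy women, up to 0.25 mg/kg) report no serious or severe AEs, which does not suggest toxicity rates of 40%.

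All of that stands, and it rules out several stronger readings that a reader might infer:
- That 14.1 excludes symptom-free abnormalities outright. It leaves them to judgement.
- That all dose holds depend on AEs. The hemoglobin rows do not.
- That kidney data are lost. BUN, creatinine, urine protein and microalbumin are collected, summarised and listed; they are not counted by grade.
- That DLT rates are biased downward, or that an escalation decision was wrong. The documents show only that an under-count is possible.

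The safeguards nevertheless leave the gap in place. Pre-dose review points back to Section 10.8, where a non-hemoglobin laboratory value has no row of its own. Section 10.8.4 is discretionary. The team's access to results does not alter the DLT or Grade ≥3 tables in the report.

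**Conclusion.** The point holds in a limited form. A laboratory value at DLT grade, without symptoms, not leading to discontinuation and not judged clinically relevant, may be missing from the DLT and Grade ≥3 counts. If it is transient, no planned table counts it. This follows from the text alone.

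The size is unknown. The binomial figures show only how sensitive a two-event criterion is in small cohorts: a large drop at an assumed 40% rate (77% to 34%) and a small absolute one at 10% (11% to 3%), with six patients and half of events recorded. They assume independent events, no other DLTs, and a mechanical reading of a criterion that the protocol applies only in part.

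The SAP is dated 04 August 2017 and describes the escalation cohorts in the past tense, so the point now bears mainly on how safety is reported. It is worth acting on because the remedy is cheap and uses data already collected.

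**What to change.** **SAP 5.8.1.** Add a listing, by cohort, of laboratory values that are new or worsened from baseline, reach the CTCAE grades already used in Protocol 10.6 within 28 days of the first dose, and were not reported as AEs. Leave out hemoglobin increases. Present DLT incidence alongside this listing without merging the two, since unreported values carry no relatedness assessment and cannot be called DLTs.

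**SAP 5.8.3.** Next to the end-of-treatment shift table, add a table of worst post-baseline CTCAE grade by cohort, including creatinine and, as far as the collected data can be graded, urine protein.

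**Protocol.** If it is amended for any reason, Sections 14.1 and 14.5 must be reconciled with the AE-based rules in 10.6 and 10.8.1. Any such wording should leave out hemoglobin-driven holds and reductions. Section 7.4 treats hemoglobin rises as an expected drug effect, and making them AEs could feed the rule in 10.8 on more than two dose reductions due to an AE.

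**Cost.** One listing and one table. The safety profile may look slightly less favourable. The condition of new or worsened from baseline keeps chronic disease values out.
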